**d. Study Conclusion**

The experiment terminates for each participant at the end of their surgery. no additional follow up is needed. the general surgery service will care for the patients post-operatively and manage any adverse events that may occur.

---

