### a. Procedures

Surgeons will identify patients scheduled to undergo laparoscopic surgery procedures and notify study staff. The patient will be met in the pre- operative holding area and informed consent will be obtained.

Patients will be randomized via block randomization.

Clinical information will be collected from participating patients including age, sex, demographic, past medical and surgical history, medications, allergies, diagnosis, and planned procedure. Clinical data will be de- identified and stored on a password protected spreadsheet on a PHI- safe server.

The surgeon will utilize the TPAD device to assist with Veress needle insertion (standard of care) to obtain access to the peritoneal cavity. The device will also be used to guide primary trocar placement.

Following induction of general anesthesia, the patient is prepped and draped in sterile fashion. Local anesthetic is infiltrated at the planned incision site and an incision is made with a scalpel. These steps are the same in any laparoscopic procedure. Next, the sterile TPAD, which is connected to a suction source, is centered over the incision, and the suction cups activated to non-invasively grasp the skin. The TPAD is pulled upward, and the Veress needle is advanced through the incision into the peritoneal cavity. Once the needle enters the cavity, the abdomen is insufflated as per usual standard of care. Once insufflated, the veress needle is withdrawn while maintaining the TPAD's suction on the skin. The primary trocar is then advanced through the incision into the abdominal cavity. The suction is then released and the TPAD taken away from the operating field.

The time needed to obtain laparoscopic access and the time needed for trocar placement will be recorded. Non-identifiable photos and/or video may be taken of the TPAD device during use. Acquired digital images may capture a portion of the patient's skin, however if a patient has any identifying features such as scars or tattoos, these areas will be cropped out of the images, or if this is not possible, no images will be recorded of that patient. There will be no other alterations to the planned surgery and it will proceed as planned. Following surgery, the surgeon will complete a questionnaire. Any adverse events will be recorded by medical record review.

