Patients will undergo routine postoperative care as indicated by their surgery. no additional visits will be required due to their being enrolled in the study. The patient will participate in a questionnaire and may take non-identifiable photographs of the portion of the patients skin where the TPAD device acts, as described above.

---

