**d. Use of Audio and Video Recordings**

Non-identifiable digital photos and/or videos will be taken of the TPAD during use and post-operatively. Acquired digital images may capture a portion of the patient's skin, however if a patient has any identifying features such as scars or tattoos, these areas will be cropped out of the images, or if this is not possible, no images will be recorded of that patient. Images will be kept on an encrypted, secure server, accessible only to study personnel. Some of these images may be used for publication or shared with the sponsor for providing instruction for other surgeons. Any images not used for these purposes will be erase.

---

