**m. Planned Duration of the Study**

The study duration will be 1 year.

Total time per participant:

(i) screening: 1 week

(ii) active participation: <1 day (duration of surgery)

(iii) analysis of data: 1 month

---

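### Sections 9.d and 8.m end the study at the close of surgery although later safety data are planned, and bruising, the only listed TPAD risk, has no stated assessment in either arm.

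*Protocol*

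**What the plan says.** **End of participation.** Protocol 9.d reads: "The experiment terminates for each participant at the end of their surgery. no additional follow up is needed". It continues: "the general surgery service will care for the patients post-operatively and manage any adverse events that may occur". Section 8.m agrees on the length: "ii) active participation: <1 day (duration of surgery". Its next line, "iii) analysis of data: 1 month", concerns analysis and sets no period for collecting adverse events.

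**Data due after that point.** Section 2.a says: "Any adverse events will be recorded by medical record review". It also says of routine post-operative care that "no additional visits will be required due to their being enrolled in the study", and then: "The patient will participate in a questionnaire and may take non-identifiable photographs of the portion of the patients skin where the TPAD device acts". Section 2.d adds: "Non-identifiable digital photos and/or videos will be taken of the TPAD during use and post-operatively".

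**Status of these data.** Safety is named in the study's purpose (1.a). Section 2.g makes adverse events and the patient questionnaire secondary outcomes, and 9.e puts adverse events under monitoring.

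**Bruising.** In 9.a, bruising or discoloration of the skin is the only entry in the list of TPAD risks. The SAP's sample-size paragraph says that no powered calculation was made, but treats 15 per group as enough for bruising and for device function. Section 2.g does not name bruising, and the SAP's methods paragraph covers questionnaire answers only.

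**The concern.** A study whose stated purpose includes safety needs to say over what period harms are counted, and to look for the expected device harm in every patient. Here the section that closes the study stops at the end of the operation, while the safety data come from records that continue after it. Staff who apply 9.d literally could leave later harms out. Staff who take it to mean only that there are no study visits must choose a review period themselves, and may choose differently from one patient to the next.

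Bruising is the harm most directly tied to suction on the skin. If nobody is asked to look for it, an absence of recorded bruises cannot be told apart from an absence of charting. Section 2.g also makes the project leader's safety evaluation depend on recorded device-related events, so what gets recorded matters during the study as well as in the report.

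**Working it through.** **1. When each item is collected**

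| Item | Where | Status | Time stated |
|---|---|---|---|
| Surgeon questionnaire | 2.g | primary | end of every operation |
| Access time | 2.a, 2.g | secondary | measured during the operation |
| Adverse events | 2.a, 2.g, 9.e | secondary | record review, no period |
| Patient questionnaire | 2.a, 2.g | secondary | none |
| Post-operative images | 2.d | not an outcome | after surgery, no time |

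Of the four outcomes in 2.g, two are timed and 4 − 2 = 2 are not. The patient is under general anesthesia during the operation (2.a), so a satisfaction questionnaire must in practice follow it. That is an inference, but a strong one.

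**2. The two readings of 9.d**

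- *Literal.* Nothing after surgery belongs to the study. This conflicts with the patient questionnaire and the post-operative images, and limits the record review to events during the operation.
- *No added study visits.* This fits 2.a and the second half of 9.d. The record review may then extend past surgery, but no section says how far.

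Neither reading yields a defined adverse-event period.

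**3. Every place where bruising could be captured**

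- 2.g does not name it as an outcome.
- The skin photographs in 2.a are optional. The uses that 2.d gives for images are publication and instructing other surgeons; the rest are erased. They are not described as an assessment.
- The record review in 2.a covers both arms, but finds a bruise only if routine notes mention it.
- No definition, time or assessor is given anywhere.

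**4. What incomplete charting could do (illustration only)**

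The SAP gives no bruising rate, alpha or power, so its 15 per group cannot be reproduced. Assume a true rate p and a fraction c of bruises charted. The chance of recording at least one in n patients is 1 − (1 − p·c)^n. For p = 10% and n = 15, this is 1 − 0.90^15 = 79% when c = 1, and 1 − 0.95^15 = 54% when c = 0.5.

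| Assumed p | n=15, c=1 | n=15, c=0.5 | n=10, c=1 | n=10, c=0.5 |
|---|---|---|---|---|
| 5% | 54% | 32% | 40% | 22% |
| 10% | 79% | 54% | 65% | 40% |
| 20% | 97% | 79% | 89% | 65% |
| 30% | 99.5% | 91% | 97% | 80% |

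Both sizes are shown because 2.g gives 10 per group and the SAP gives 15.

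If no bruise is recorded, the one-sided 95% upper limit on the recorded rate is 1 − 0.05^(1/n), which is 18.1% for n = 15 and 25.9% for n = 10. Dividing by c = 0.5 gives limits on the true rate of 36.2% and 51.8%. With c unknown, no limit on the true rate can be stated.

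**The case against.** The strongest reply is that 9.d has been read out of context. It goes straight on to post-operative care by the surgical service, and 2.a says that no visits are added. Together these naturally mean that there is no extra follow-up burden, and a same-day questionnaire fits within less than one day. That stands, and it reduces the conflict to one of wording. It does not supply a review period.

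The study is also an unpowered pilot, its primary outcome is collected at the end of every operation, and no test of adverse events or bruising is planned. All of that is true and limits the weight of the point.

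The questionnaire forms are not reproduced, so they may ask about bruising. This cannot be judged from the documents.

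A reader might infer more than the text supports:

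- *Photographs in the device arm alone will inflate its bruising count.* No section says that photographs are used to detect bruising; the uses given in 2.d are others.
- *The SAP plans a bruising comparison with control.* Its phrase about the control group may attach only to device function, and no such test is described.
- *Uneven review will favor one arm.* Patients are randomized in blocks (2.a). Differences in routine care across the broad indications in 8.a make the review less uniform, but they are not shown to favor either arm.

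**Conclusion.** The point holds as a conflict of wording with a practical consequence. Read literally, 9.d and 8.m cut off safety data that 2.a, 2.d and 2.g expect. Read generously, they leave the adverse-event period unstated. Separately, the only risk listed for the device has no stated assessment in either arm, although the SAP relies on it when discussing sample size.

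It would go too far to say that later harms will be missed: the documents do not show this, and the record review may well pick them up. Nor is the missing questionnaire time a serious flaw in itself; it is a detail to fill in.

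The size is two of four outcomes without a stated time and one device-specific harm without systematic capture. The probabilities in the illustration rest on assumed bruising rates of 5% to 30% and an assumed charting fraction of one half. They show direction and scale, and are not predictions. The primary outcome is unaffected.

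**What to change.** 1. Reconcile 9.d and 8.m with 2.a, 2.d and 2.g so that only the intervention ends at surgery, and data collection continues as those sections describe.
2. Record access-site bruising as yes or no for every patient, in both arms, at the end of surgery.
3. Apply one fixed adverse-event record-review window, identical in both arms, with its length set by the investigators. Section 9.c has the study key deleted at the study's conclusion, so the review should be finished before then.

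The cost is a wording amendment, one yes/no entry per patient (20 under 2.g; 30 under 8.a and the SAP) and a slightly longer chart review. No visits are added.

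Two limits remain. The person who records bruising will know the arm. Bruising that appears after the end of surgery will still depend on charting, though over the same window in both arms.

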**e. Data Safety Monitoring Plan (DSMC)**

- i. Data and/or events subject to review

Aggregate Data Analysis  
Progress toward Study endpoint(s)  
AEs, SAEs, SUSARs  
Participant consent forms

- ii. Person(s) responsible for Data and Safety Monitoring

The PD will be responsible for Data and Safety Monitoring.

- iii. Frequency of DSMB meetings

N/A

---

**10. BENEFITS**

We anticipate the TPAD could save anywhere from 1 to 10 minutes of anesthesia time. the patient may therefore benefit from shorter operative time (shorter duration of anesthesia). There could additionally be significant cost savings with shorter anesthesia. For example, the average cost for running an OR has been estimated at \$62/minute, not counting personnel costs including Anesthesia fees. Therefore, we anticipate the potential for significant time and cost savings.

---

**11. PRIVACY AND CONFIDENTIALITY**

All participant information and specimens are handled in compliance with the Health Insurance Portability and Accountability Act (HIPAA) and privacy policies of Stanford University, Stanford Health Care, and Stanford Children's Health.

Pilot Study to Establish Safety and Ease of Use of a TauTona Pneumoperitoneum Assist Device (TPAD) for Laparoscopic Surgery

NCT04392635

August 19, 2024

Statistical Analysis Plan

Statistical Methods

For surgeon and patient questionnaire answers, a Wilcoxon test will be performed for each answer against a theoretical median of 4.0 (best). Since the insertion of the Veress needle should not significantly impact the final outcome of the entire laparoscopic procedure, analysis assumes that the theoretical median for each answer should be 4.0. Further, the standard of care is assumed to provide the current best care, so its theoretical median should be 4.0.

Determination of Sample Size

There were no statistically powered sample size requirements for this study. Based on the end points, the sample size of 15 for each group would be sufficient to determine bruising and the ability of the TPAD device to function as intended as compared to the control group.

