### a. Brief Summary

The purpose of this study is to assess the safety and ease of use of a trocar placement access device (TPAD, Tautona) for laparoscopic surgery. 10 patients will undergo laparoscopic surgery as planned, with their surgeon using the TPAD device to guide Veress needle insertion and primary trocar placement while gaining access to the peritoneal cavity. Surgeons will complete a questionnaire following use of the TPAD to evaluate the device feasibility. Ten patients will undergo standard of care without use of the TPAD device and also complete surveys.

---

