**g. Study Endpoint(s)**

The study will terminate after 10 patients have been enrolled and have undergone surgery with use of the study device and 10 patients have undergone the standard of care and completed the survey. The primary outcome measure is device feasibility as measured by a surgeon questionnaire, which is completed at the end of every surgery. Secondary outcome measures include the time needed to obtain laparoscopic access using the device, as well as monitoring for adverse events. Another secondary outcome measure includes patient questionnaire to assess satisfaction.

If there is clear evidence of a lack of device feasibility through surgeon questionnaire review, or if there are any adverse events recorded that are related to the device and which endanger the health of a patient, the project leader will evaluate this information and decide whether any modifications or termination of the protocol are indicated.

---

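### The primary questionnaire analysis tests each answer against 4.0, the score labelled best: at a ceiling the signed-rank test does not control error for a median of 4.0, and no test compares the randomized arms

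*SAP*

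**What the plan says.** Protocol section 2.g makes the surgeon questionnaire primary: "The primary outcome measure is device feasibility as measured by a surgeon questionnaire, which is completed at the end of every surgery". A patient satisfaction questionnaire is secondary.

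The SAP's Statistical Methods paragraph gives one procedure for both questionnaires: "a Wilcoxon test will be performed for each answer against a theoretical median of 4.0 (best"). It explains that "analysis assumes that the theoretical median for each answer should be 4.0", and for the comparator that "the standard of care is assumed to provide the current best care, so its theoretical median should be 4.0". The comparator is a fixed value, so this is the one-sample signed-rank test. The SAP names no other test, and the protocol has no statistical section.

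The design has a concurrent control. Protocol 2.a says "Patients will be randomized via block randomization", and 1.a says "Ten patients will undergo standard of care without use of the TPAD device and also complete surveys". The SAP's sample-size paragraph disclaims a power basis, gives 15 per group, and refers to "the ability of the TPAD device to function as intended as compared to the control group". Protocol 1.a and 2.g give 10 per group.

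No success threshold is attached to the p-value. Section 2.g has the project leader consider changing or ending the protocol "If there is clear evidence of a lack of device feasibility through surgeon questionnaire review".

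**The concern.** A one-sample signed-rank test asks whether values are spread symmetrically about the null. When the null is the highest possible score, differences can only be zero or negative, so the symmetry assumption cannot hold unless every answer is 4. A distribution can have a true median of 4 with up to half its answers below 4, and the test may still reject.

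Neither result answers the feasibility question. Rejection can only mean that answers fall below the best score. Non-rejection in a small, unpowered sample does not show that the device is feasible.

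The control arm was randomized, yet its expected score is assumed rather than estimated. Testing each arm against the same constant does not compare them. What is at stake is a misleading primary result reaching the people who review the questionnaires.

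**Working it through.** **Inputs.** Null value 4.0, labelled best (SAP, Statistical Methods). n = 15 per group (SAP, Determination of Sample Size) or 10 per group (Protocol 1.a and 2.g). Assumed because the documents do not say: 4.0 is the maximum, two-sided alpha is 0.05, and answers are independent. The SAP's 15 per group has no power basis, so there is no figure to reproduce.

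**Step 1: the exact p-value.** Let k ≥ 1 be the number of answers below 4. All k non-zero differences are negative, so the positive rank sum is 0, the most extreme of 2^k equally likely sign patterns. Hence two-sided p = 2 × (1/2)^k = 2^(1−k):

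- k = 4: 0.125
- k = 5: 0.0625
- k = 6: 0.031

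Neither n nor the size of the shortfalls enters. Enumerating the sign flips gives the same values with zeros dropped or Pratt-ranked, and for mixed shortfalls: −1, −1, −1, −3 gives 0.125, and −1, −1, −1, −3, −3 gives 0.0625. The test therefore rejects when k ≥ 6. At n = 15 the median is the eighth ordered answer, so with k = 6 or 7 the sample median is still 4.

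**Step 2: rejection when the true median is 4.** Let q be the probability that an answer is below 4, with q < 0.5. The rejection probability is P(Binomial(n, q) ≥ 6).

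| q | n = 15 | n = 10 |
|---|---|---|
| 0.1 | 0.2% | 0.01% |
| 0.2 | 6.1% | 0.6% |
| 0.3 | 27.8% | 4.7% |
| 0.4 | 59.7% | 16.6% |

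At n = 15 and q = 0.4, rejection with a sample median of 4 has probability P(k = 6) + P(k = 7) = 0.2066 + 0.1771 = 0.384. At n = 10, an exact rejection needs six answers below 4, so the sample median is then below 4.

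**Step 3: unstated software choices.** The SAP does not say exact or approximate, corrected or uncorrected, or how zeros are handled. Normal-approximation cut-offs at n = 15 with equal shortfalls:

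- uncorrected: k = 4 (p = 0.0455)
- continuity-corrected, zeros dropped: k = 5 (p = 0.037; k = 4 gives 0.072)
- continuity-corrected, Pratt ranks: k = 4 (p = 0.0497)

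At q = 0.4, a cut-off of 5 rejects 78.3% of the time at n = 15 and 36.7% at n = 10. A cut-off of 4 rejects 90.9% and 61.8%. With unequal shortfalls (−1, −2, −3 with probabilities 0.2, 0.1, 0.1), the approximate versions reject between 63.7% and 90.9% at n = 15, and between 21.0% and 61.8% at n = 10. None is below the exact test.

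**Step 4: two one-sample tests are not a comparison.** With identical arms, n = 15 and q = 0.4, exactly one arm is flagged with probability 2 × 0.5968 × 0.4032 = 0.48. By contrast, a two-sided between-arm rank-sum test was simulated (4,000 replicates) with both arms at 60% scoring 4, 30% scoring 3 and 10% scoring 2. It rejected in 4.7% of trials at n = 15 per arm and 4.3% at n = 10.

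**The case against.** - **It is an unpowered pilot with no decision tied to p.** This is true, and it limits the harm: a significant result does not by itself end or validate anything. It does not make the only stated primary analysis valid.
- **The error runs against the device.** Rejection can only flag a shortfall, so this test cannot yield a false claim of superiority. The SAP also never says non-rejection shows feasibility. Both points stand; the SAP simply gives neither result a meaning.
- **The large figures need many answers below 4.** The documents give no basis for 40%, and the SAP expects a median of 4.0. At 10% below 4 the exact test almost never rejects. That is not error control: the rejection rate runs from near zero to far above 5% while the stated null remains true.
- **At the protocol's 10 per group, the exact test is mild.** It stays under 5% up to 30% below 4. This holds for the exact version only; an uncorrected approximation rejects from k = 4.
- **The test could be read as targeting the pseudomedian.** This falls below 4 once (1 − q)² < 0.5, that is q > 0.293, so rejections at 30% or 40% would be correct for that quantity. But the SAP says median, and just under that bound exact rejection at n = 15 is still P(Binomial(15, 0.293) ≥ 6), about 26%.
- **A between-arm test may not be possible for every item.** The SAP's reference to the control group concerns bruising and device function, and device-specific questions may not apply to controls. This stands, and it limits the comparison to questions asked in both arms.

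**Conclusion.** The concern holds. With 4.0 as the top score, the planned test does not control error for the null the SAP states, and its exact p-value only counts how many answers miss 4. The excess is substantial at the SAP's 15 per group once about 30% of answers fall below 4. It is smaller at the protocol's 10 per group, where the exact version exceeds 5% only above about 30%. No between-arm test of the answers is specified despite randomization.

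The sizes rest on the assumed 5% two-sided level, independent answers and the chosen shares below 4. The symmetry failure needs only that 4.0 is the maximum, which rests on the SAP's own label because the questionnaire is not shown. The consequence is a misleading primary result put before a judgement-based review, not an automatic wrong decision. It should still be corrected, because this is the whole primary analysis and the change is small.

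**What to change.** Delete the one-sample Wilcoxon test against 4.0 and replace it with the following.

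1. For each question and arm, report the count at each score and the proportion scoring 4 with an exact (Clopper-Pearson) 95% confidence interval. For scale: 10/15 gives 38% to 88%, 15/15 gives 78% to 100%, and 10/10 gives 69% to 100%. Read the proportion with the full distribution, since alone it ignores how low the other scores are.
2. State that a non-significant p-value is not evidence of feasibility. If a feasible/not-feasible statement is wanted, the sponsor should define it on these summaries before the answers are analysed; otherwise label the results descriptive.
3. Report the number of surgeons and the forms per surgeon, because the intervals assume independent answers.
4. Let any hypothesis test of the answers compare the randomized arms, on questions asked in both, labelled exploratory because the study is not powered.

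The cost is SAP wording and one extra tabulation, with no new patients or questionnaire items. The downsides are that the primary outcome no longer has a single p-value against a fixed target, the intervals at 10 to 15 per arm are wide, and device-only questions cannot be compared between arms. Keeping the test as a descriptive aside beside the score counts would reduce the harm, but would leave in print a p-value that is not valid for the stated null.

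### The primary outcome is a surgeon questionnaire, but the SAP tests every answer separately against 4.0 and names no primary measure or feasibility criterion, so the plan gives no answer on feasibility

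*SAP*

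**What the plan says.** Protocol section 2.g states: "The primary outcome measure is device feasibility as measured by a surgeon questionnaire, which is completed at the end of every surgery". The same section makes the patient questionnaire secondary: "Another secondary outcome measure includes patient questionnaire to assess satisfaction". It gives no item, total or threshold. Its only decision language on the questionnaire is a review by the project leader if the device clearly proves not feasible, with no number attached.

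The SAP, under Statistical Methods, treats the surgeon and patient questionnaires alike: "a Wilcoxon test will be performed for each answer against a theoretical median of 4.0 (best". The reference value is a premise, not an estimate. The SAP says "analysis assumes that the theoretical median for each answer should be 4.0", and of the control treatment that "the standard of care is assumed to provide the current best care, so its theoretical median should be 4.0". It states no significance level, sidedness, exact or approximate version of the test, number of items, order of testing or rule for combining item results. It describes no questionnaire comparison between the two randomised arms.

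**The concern.** A primary outcome needs one measure and one criterion. Here the primary surgeon items and the secondary patient items pass through the same item-by-item test, so the Protocol's ranking of the two disappears in the analysis. If two surgeon items came out significant and the rest did not, nothing in either document says whether the device is feasible. That judgement would be made after the results were seen.

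The test itself adds to the difficulty. If 4.0 is the highest possible score, an item can only fall short, and each further item is another chance to be flagged. In the other direction, an item on which half the surgeons' answers are below best can go unflagged. The same list could therefore feed unwarranted alarm or unwarranted reassurance. The randomised control arm, the natural yardstick, is replaced by an assumed value.

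**Working it through.** **The plan's own figure.** There is none to reproduce. The SAP gives 15 per group and says that this was not set by a power calculation; no error rate is stated.

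**Inputs from the documents.** The reference median is 4.0, labelled best (SAP, Statistical Methods). The size per arm is 10 (Protocol 1.a and 2.g) or 15 (SAP, Determination of Sample Size). That difference is a separate matter, so both sizes are shown.

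**Assumptions, because the documents are silent.** 4 is the scale maximum. The test is an exact one-sample signed-rank test, two-sided at 0.05, run within an arm. Answers from different operations are independent. A share *q* of answers falls below 4, with *q* under 0.5 so that the true median is still 4.0. There are *m* items, independent of each other.

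**Step 1: when is an item flagged?** Answers equal to 4 give zero differences and drop out. The other *k* differences are all negative, so the exact two-sided p-value is 2 × 0.5^k, whatever the ties or the size of the shortfall.

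- k = 5: 2 × 0.03125 = 0.0625, not flagged
- k = 6: 2 × 0.015625 = 0.031, flagged

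So an item is flagged when six or more answers are below 4. Five of 10 below best is not significant, even if all five are the lowest possible score.

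**Step 2: chance that one item is flagged,** p₁ = P(Binomial(n, q) ≥ 6). **Step 3: chance of at least one flag among *m* items,** 1 − (1 − p₁)^m.

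| n per arm | q below 4 | one item | 5 items | 10 items |
|---|---|---|---|---|
| 10 | 0.2 | 0.006 | 0.031 | 0.062 |
| 10 | 0.3 | 0.047 | 0.215 | 0.384 |
| 10 | 0.4 | 0.166 | 0.597 | 0.838 |
| 15 | 0.2 | 0.061 | 0.270 | 0.467 |
| 15 | 0.3 | 0.278 | 0.804 | 0.962 |

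For example, at n = 10 and q = 0.3: 1 − (1 − 0.0473)^10 = 0.384.

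**Step 4: sensitivity to the unstated version of the test.** Take n = 10, q = 0.2 and 10 items. The exact two-sided test gives 0.062. The exact one-sided test flags from k = 5 (p = 0.031) and gives 0.284. A two-sided normal approximation without continuity correction, with all shortfalls equal, flags from k = 4 (p = 0.0455) and gives 0.724.

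**Step 5: would a multiplicity correction cure it?** With 5 items, Bonferroni tests each at 0.01 and needs k ≥ 8 (2 × 0.5^8 = 0.0078). At q = 0.4 the chance of at least one flag is then 0.060 at n = 10 but still 0.698 at n = 15. The fixed reference at the ceiling drives much of the result: at n = 15 and q = 0.3, a single item is already flagged 27.8% of the time.

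**The case against.** The strongest reply is that this is an unpowered pilot. The SAP states no significance level and makes no confirmatory claim, so control of the family-wise error rate is not an established requirement. That stands. It does not supply the missing primary measure, which a pilot also needs.

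A reader might infer that the plan carries the familiar family-wise error of 1 − 0.95^m: 23%, 40% or 64% for 5, 10 or 20 items. The documents do not support this. The signed-rank null is symmetry about 4.0. If no answer can exceed 4, that holds only when every answer is 4, and then no item can be flagged however many there are. The 5% per-item error behind those figures does not exist for this test. It is also arguable whether a flag at q = 0.3 is false at all, since such answers do fall short of best.

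It is fair, too, that the figures above rest on several assumptions and vary widely with them. Items rated by one surgeon on one operation are unlikely to be independent, and positive correlation lowers the chance of at least one flag.

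Finally, the questionnaire is not reproduced. Some surgeon items may concern only the device, and the items may not average sensibly. This limits how closely a fix can be prescribed, but it does not answer the point.

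**Conclusion.** The point holds and should be acted on. Its core needs no assumed figure: the primary outcome is a questionnaire, every answer is tested separately, and neither document says which answer, score or pattern of results means feasible.

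The size of the second effect is a range. Under the stated assumptions, with 10 independent items and 10 per arm, the chance of at least one flagged item while the true median is 4.0 runs from about 6% (20% of answers below 4) to 84% (40% below). At 15 per arm it is 47% at 20% and 96% at 30%.

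A reader might take the 96% as this trial's error rate, or conclude that a multiplicity adjustment is the remedy. Neither follows. The 96% is one combination of unstated inputs, and a good part of it comes from placing the reference at the assumed top of the scale, which an adjustment does not remove.

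**What to change.** Rewrite the Statistical Methods paragraph of the SAP, before analysis, to do the following:

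- **Name one primary surgeon measure.** Use either a single overall item or the per-case mean of items that share a scale and apply in both arms. The choice depends on the questionnaire, which the sponsor holds. Section 2.g has it completed after every surgery, so control-arm answers should exist; confirm this.
- **Compare the arms.** Report the difference between the randomised arms with a 95% confidence interval, for example a Hodges-Lehmann estimate with the rank-sum test, in place of the test against 4.0.
- **State the criterion.** Say in advance what result counts as feasible. Without it, an interval alone would leave the question as open as the list of p-values does.
- **Describe the rest.** Summarise device-only items in the TPAD arm. Report all other surgeon items and the patient questionnaire as distributions with intervals, without significance claims. No alpha adjustment is then needed.

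The cost is one SAP paragraph, with no new data and no larger sample. Individual items lose their significance label, and the interval will be wide at 10 to 15 per arm.
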